9.3 Immunogenicity

Anti-drug (UCB6114) antibody status and classification, changes from Baseline in titer over time and the incidence of treatment-emergent ADA positivity are exploratory immunogenicity endpoints in Part A of this study. Potential relationships between ADA and PK, PD, antitumor activity and safety will also be explored but this will be reported separately outside of the CSR.

Serum samples will be collected from all study participants for the measurement of ADA and the evaluation of immunogenicity according to the Schedule of Activities in the protocol.

All listings of ADA will be presented for the SS and summaries of the ADA data will be presented by treatment group for the ADAS.

Anti-drug (UCB6114) antibodies will be measured using a three-tiered assay approach: Screening assay, confirmatory assay and titration assay.

Samples will first be evaluated in the Screening assay using a false positivity rate of 5% (reported as ‘negative screen’ or ‘positive screen’), followed by analysis of screened positive samples in the confirmatory assay (which is a drug depletion assay) to confirm the positivity of the samples (reported as ‘negative immunodepletion’ or ‘positive immunodepletion’). Samples that are confirmed as positive in the confirmatory assay will be evaluated in a titration assay to assess the ADA level and this will be reported as titer (reciprocal dilution factor including minimum required dilution).

Anti-drug (UCB6114) antibody sample status will be determined as follows from the pre-treatment sample taken on Day 1 of Cycle 1 (Baseline) and all post-treatment (post-Baseline) samples.

- Sample values that are either ‘negative screen’ or ‘positive screen’ and ‘negative immunodepletion’ will be defined as **ADA negative**
- Sample values that are ‘positive screen’ and ‘positive immunodepletion’ will be defined as **ADA positive**

Anti-drug (UCB6114) antibody sample status will be listed for each participant at each visit by treatment group. This listing will include sampling dates and times, the Screening assay result, the confirmatory assay result and the derived ADA sample status. In addition, the titer from the titration assay (if applicable) will be listed together with the change from Baseline in titer. The number and percentage of participants with a positive or negative sample at each visit will be summarized by treatment group. Percentages will be calculated based on the number of participants with a non-missing/sufficient sample at the visit.

Based on the ADA status of the samples, study participants will be categorized according to the following 6 ADA classifications in Table 9-3:

Table 9-3: ADA Classifications

Classification	Classification Label	Definition
1	Pre-ADA negative – treatment induced ADA negative	Includes participants who have an ADA negative status at Baseline, or missing/insufficient Baseline sample, and an ADA negative status at all sampling timepoints post-Baseline (including SFU). Participants with missing post-Baseline samples are included as long as the missing samples do not result in an unmonitored period greater than 16 weeks.
2	Pre-ADA negative – treatment induced ADA positive	Includes participants who have an ADA negative status at Baseline, or missing/insufficient Baseline sample, and an ADA positive status at any sampling timepoint post-Baseline (including SFU).
3	Pre-ADA positive – treatment reduced ADA	Includes participants who have an ADA positive status at Baseline and an ADA negative status at all sampling timepoints post-Baseline (including SFU)
4	Pre-ADA positive – treatment unaffected ADA	Includes participants who have an ADA positive status at Baseline and an ADA positive status at any sampling timepoint post-Baseline (including SFU) with titer values of the same magnitude as Baseline (≤ 1.80 -fold difference from the Baseline value) or with decreased titer values compared to Baseline (> 1.80 -fold decrease from the Baseline value).
5	Pre-ADA positive – treatment boosted ADA positive	Includes participants who have an ADA positive status at Baseline and an ADA positive status at any sampling timepoint post-Baseline (including SFU) with increased titer values compared to Baseline (> 1.80 -fold increase from the Baseline value).
6	Inconclusive	Includes participants who do not satisfy the criteria for classifications 1-5

ADA=anti-drug (UCB6114) antibody; SFU=Safety Follow-up.

Note: The terminology 'treatment unaffected' is ambiguous as the criteria refers to ADA responses that are not increased upon dosing compared to Baseline level whereas titers may reduce.

A study participant will be classified as having **treatment-emergent ADA positivity** if they satisfy one of the following criteria:

- The Baseline result is ADA negative and at least one post-Baseline result is ADA positive (pre-ADA negative – treatment induced ADA positive) – ADA classification 2 in Table 9-3;
- The Baseline result is ADA positive and at least one post-Baseline result shows a pre-defined fold increase in titer from the Baseline value (the fold increase from Baseline required to meet this criterion will be defined with the development of the assay and will be included in the TFLs) (pre-ADA positive – treatment boosted ADA positive) – ADA classification 5 in Table 9-3.

Total anti-drug (UCB6114) antibody **incidence** will be determined by the number and percentage of participants with treatment-emergent ADA positivity (as defined above). The denominator for the percentage calculation will be the number of participants with at least one available/reported post-Baseline result.

Total **prevalence** of pre-anti-drug (UCB6114) antibody will be determined by the number and percentage of participants who are pre-ADA positive (i.e. participants who have a positive ADA status at Baseline). The denominator for the percentage calculation will be the number of participants with an available/reported Baseline sample result.

Total anti-drug (UCB6114) antibody **prevalence** will be determined by the number and percentage of participants with ADA classifications 2, 4 and 5 in Table 9-3 (i.e. an ADA positive status at any post-Baseline sampling timepoint). The denominator for the percentage calculation will be the number of participants with at least one available/reported sample result (either at Baseline and/or post-Baseline).

The ADA classification for each participant will be listed by treatment group. This listing will also include whether or not the participant achieved treatment-emergent ADA positivity (ADA incidence), whether the participant was pre-ADA positive (pre-ADA prevalence) and whether the participant had an ADA positive status at any post-Baseline sampling timepoint (ADA prevalence). In addition, the visit at which the participant first achieved treatment-emergent ADA positivity will be included.

The number and percentage of participants in each of the 6 ADA classifications defined above in Table 9-3 will be presented by treatment group. Also, in this tabulation, ADA incidence and prevalence (as defined above) will be summarized.

The first occurrence of treatment-emergent ADA positivity (based on the criteria above) will be summarized using frequency counts and percentages at each post-Baseline visit by treatment group. This tabulation will include a count of the number of participants at each post-Baseline visit who fulfill at least one of the above defined criteria for treatment-emergent ADA positivity; participants will be counted in the numerator based on the earliest visit at which one of these criteria is fulfilled. At other visits, participants will be counted in the denominator (assuming an assessment of treatment-emergent positivity is available) and this will be used in the percentage calculations.

Individual study participant ADA titer profiles over actual time will be presented graphically on the linear and the semi-logarithmic scale. The linear scale plots will be repeated for the subset of participants who achieve treatment-emergent ADA positivity during Part A.

Mean (\pm standard deviation) C_{min} will be plotted by ADA sample status over scheduled time with treatment groups overlaid on the same plot.

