2.3 Study design and conduct

Study ONC001 is a multicenter, nonrandomized, open-label, Phase 1/2 study evaluating the safety, PK, efficacy (as assessed by antitumor activity), PD, biomarkers, and immunogenicity (ADA activity) of intravenous (iv) UCB6114 as monotherapy and in combination with selected standard of care (SoC) regimens in study participants with advanced solid tumors.

The study has a modular design including up to 3 dose escalation modules (Parts A, B, and C), 1 dose adaptation module (Part A1), and up to 4 dose expansion modules (Parts D, E, F, and G). Depending on emerging data, not all modules may open. This SAP is focused only on the first dose escalation module of the study (Part A).

[figure not shown]
Part A consists of a Screening Period (28 days), a Treatment Period (consisting of 28-day cycles), an SFU visit (approximately 30 days after the last dose of study treatment) and a Final Visit (approximately 3 months after the last dose of study treatment). The planned duration of study treatment is 2 cycles. Participants may remain on study for additional cycles if they are receiving therapeutic benefit or until they fulfill one of the criteria for study discontinuation.

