3.2.2 Study periods

Part A of the study will consist of the following study periods:

- Screening Period – up to 28 days;

- Treatment Period – Successive 28-day cycles of study treatment (Q2W dosing on Day 1 and Day 15 of each cycle continuing until disease progression, unmanageable toxicity, or participant withdrawal). Within the first cycle of the Treatment Period, a 28-day DLT Observation Period is defined to determine safety events for dose escalation decisions. If a study participant is a sentinel participant in the cohort, there is an initial DLT Observation Period of 16 days, after which the cohort may be opened for further enrollment;
- Safety Follow-up Period – up to 30 days after the last dose of study treatment.

There will be a further extended follow-up period, up to 3 months after the last dose of study treatment, at which time the Final Visit will be performed.

For each participant, the end of the Treatment Period is defined by the date of their last dose of study treatment.

The end of Part A of the study is defined by the date of the Final Visit for the last participant (3 months after the last participant's last dose of study treatment), or the date of the SFU visit, if they discontinue prior to attending the Final Visit, or their last contact date if they discontinue early from the study without attending the SFU visit.

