3.3 Definition of Baseline values

Baseline in Part A will be the last available value prior to the first dose of study treatment. Both scheduled and unscheduled values, as well as any repeated values, should be used when defining Baseline.

Measurement-specific Baseline definitions are presented in Table 3-1.

Table 3-1: Definition of Baseline

Measurement	Definition of Baseline
Echocardiogram (LVEF) PD biomarkers from tissue (optional tumor biopsies) Tumor assessments (antitumor activity)	Screening value
12-lead ECG Physical examination and weight Vital signs Clinical laboratory data ECOG performance status	Predose value obtained on Cycle 1, Day 1, or, if missing, Screening value
Serum and urinary markers of bone turnover Circulating Gremlin-1 (cGremlin-1) Immunogenicity (ADA)	Predose sample value obtained on Cycle 1, Day 1

ADA=anti-drug (UCB6114) antibody; ECG=electrocardiogram; ECOG=Eastern Cooperative Oncology Group; LVEF=left ventricular ejection fraction; PD=pharmacodynamic.

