3.5.5 Anti-drug Antibody Set (ADAS)

The Anti-drug Antibody Set (ADAS) consists of all study participants in the SS who have at least 1 evaluable ADA assessment.

Immunogenicity analyses will be performed for the ADAS.

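### Total ADA prevalence counts Baseline-only participants in a denominator whose numerator needs a post-Baseline positive, and ADA class 1 does not state that any post-Baseline result is needed

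*SAP*

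**What the plan says.** The Part A SAP (Section 9.3, Table 9-3) and the Part A1 SAP (Section 9.3, Table 9-2) use the same six ADA classes.

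- **Class 1.** Baseline is negative or missing, with "an ADA negative status at all sampling timepoints post-Baseline (including SFU"). The next sentence relaxes this: "Participants with missing post-Baseline samples are included as long as the missing samples do not result in an unmonitored period greater than 16 weeks".
- **Class 6 (Inconclusive).** It takes whoever fails classes 1 to 5.
- **Analysis set.** Section 3.5.5 of both SAPs admits treated participants "who have at least 1 evaluable ADA assessment". The assessment need not be post-Baseline. Part A1 adds what makes a result evaluable, but not when it must be taken.
- **Incidence.** Treatment-emergent positivity (classes 2 and 5), over participants who have a post-Baseline result.
- **Total prevalence.** Classes 2, 4 and 5, described as positive at some post-Baseline timepoint, over participants "with at least one available/reported sample result (either at Baseline and/or post-Baseline").

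On timing, Section 2.3 of the Part A SAP states "The planned duration of study treatment is 2 cycles", and Part A1 plans the same number of cycles. Part A has "Successive 28-day cycles of study treatment (Q2W dosing on Day 1 and Day 15 of each cycle") and "an SFU visit (approximately 30 days after the last dose of study treatment"). The ADA Baseline is "Predose sample value obtained on Cycle 1, Day 1" (Section 3.3).

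**The concern.** A participant with only a Baseline sample gives no information on whether treatment induced antibodies. The prevalence rule nevertheless counts that participant as a post-Baseline non-positive, because someone who was never sampled after Baseline can enter the denominator but never the numerator. Incidence, shown in the same tabulation, leaves such a participant out. Every participant counted for incidence (classes 2 and 5) is also counted for prevalence (classes 2, 4 and 5), so a reader expects prevalence to be at least as high. The mismatched denominators can reverse that order.

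Class 1 raises the same question. If nothing requires a post-Baseline result, and the only limit on missing samples is longer than the planned observation window, an unsampled participant can be reported as antibody negative. Cohorts are small (3 to 6 evaluable in Part A, up to 8 in Part A1), so one participant is between 1/8 = 12.5 and 1/3 = 33.3 percentage points of a cohort's class percentages.

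**Working it through.** **1. Prevalence against incidence**

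Let m be the participants with at least one post-Baseline result, b those with a Baseline result only, and n2, n4, n5 the class counts. From Section 9.3:

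- incidence = (n2 + n5) / m
- prevalence = (n2 + n4 + n5) / (m + b)

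Prevalence falls below incidence when n4 × m < b × (n2 + n5). With no class 4 participants and at least one treatment-emergent positive, a single Baseline-only participant is enough.

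Illustrations, with one class 2 participant in a cohort of six and the Baseline-only count assumed because the SAPs give no figure:

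| Baseline-only (b) | m | Prevalence as written | Incidence, and prevalence on m |
|---|---|---|---|
| 0 | 6 | 1/6 = 16.7% | 1/6 = 16.7% |
| 1 | 5 | 1/6 = 16.7% | 1/5 = 20.0% |
| 2 | 4 | 1/6 = 16.7% | 1/4 = 25.0% |
| 3 | 3 | 1/6 = 16.7% | 1/3 = 33.3% |

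**2. Can the 16-week limit exclude a planned two-cycle participant?**

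The limit is 16 × 7 = 112 days; the SAPs give no derivation for it. The longest possible gap from first dose to Safety Follow-up (SFU) is (last dose day − 1) + 30. Dosing schedules come from Section 3.2.2 of the Part A SAP and Section 2.3 of the Part A1 SAP.

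| Schedule, 2 cycles | Last dose | Span to SFU | Over 112 days? |
|---|---|---|---|
| Part A; Part A1 Cohorts 1 and 2 (Q2W, 28-day cycle) | Day 43 | 42 + 30 = 72 days (10.3 weeks) | No |
| Part A1 Cohort 3 (Q3W, 21-day cycle) | Day 22 | 21 + 30 = 51 days (7.3 weeks) | No |
| Part A1 Cohort 4 (Q4W, 28-day cycle) | Day 29 | 28 + 30 = 58 days (8.3 weeks) | No |

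Two Q2W variants do not change this:

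- All three later doses 7 days late: 42 + 21 + 30 = 93 days.
- Three full cycles, last dose Day 71: 70 + 30 = 100 days.

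The limit first bites with a dose on Day 85: 84 + 30 = 114 days. That is the 7th Q2W, 5th Q3W or 4th Q4W dose.

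**3. Consequence for class 1**

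Section 3.5.5 admits the Baseline-only participant. Table 9-3 (Part A) and Table 9-2 (Part A1) state no minimum of post-Baseline results, and up to SFU the gap rule cannot remove anyone treated for the planned two cycles or fewer. Read literally, a negative Baseline followed by no sample is class 1.

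In the last row of the first table, with all Baseline-only participants negative at Baseline, class 1 is (2 + 3)/6 = 83.3% as written. Among those sampled after Baseline it is 2/3 = 66.7%.

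**The case against.** - **The ADA schedule is not visible.** Sampling follows the protocol's Schedule of Activities, and the tables include SFU without saying it is the last sample. The start and end of the unmonitored period are also undefined. If it ran to a Final Visit 90 days after the last dose, two-cycle spans would be 42 + 90 = 132 days (Q2W) and 28 + 90 = 118 days (Q4W), both over the limit, and 21 + 90 = 111 days (Q3W), just under. If the Final Visit were at 120 days, as the 150-day serious-event window in Section 8.2 implies (150 − 30), all three would exceed it. This stands: the timing argument is conditional on SFU being the last ADA sample.
- **Class 1 can be read more narrowly.** The missing-sample sentence may relax only the word all while still presuming some negative post-Baseline result. Part A1 also bases its class percentages on participants whose classification is not missing. As class 6 catches everyone who fails classes 1 to 5, that hints that some participants may be left unclassified. This too stands: the text is ambiguous, and the Baseline-only result is its literal reading, not its only one.
- **The limit works for longer treatment.** Treatment may continue while there is benefit, and exposure is tabulated beyond four cycles. A reader might infer that the limit is idle for everyone and should be replaced. The arithmetic does not support that, since it operates from a Day 85 dose onward. Accepting a single SFU result in its place would admit a long-treated participant with no other sample.
- **Class 6 still has members.** A reader might infer that it is emptied. Class 3 has no missing-sample allowance, so a Baseline-positive participant without later samples most naturally falls into class 6, as do long-treated participants with large gaps.
- **Few participants may be affected.** Early withdrawals are asked to return for SFU (Section 4.4 in Part A, 4.6 in Part A1), so Baseline-only status means missing that visit as well. Three of six is an illustration, not a forecast.

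None of this touches the prevalence denominator, which both SAPs state explicitly.

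**Conclusion.** The prevalence defect holds in both SAPs without any assumption about the sampling schedule. As soon as a cohort has a Baseline-only participant and a post-Baseline positive, prevalence is diluted by the factor m/(m + b), and it can fall below incidence. It would be too strong to say that the same positives yield two rates, because prevalence adds class 4 and is a separately defined quantity. The fault lies in the denominator.

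The class 1 defect holds on the literal text, and the idle 16-week limit holds for planned two-cycle participants if SFU is the last ADA sample. How many participants are affected cannot be determined from the SAPs.

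The consequence is moderate. Immunogenicity is exploratory with no hypothesis test, individual results are listed, by-visit percentages use only participants sampled at that visit, and treatment-emergent incidence is unaffected.

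**What to change.** In Section 9.3 of both SAPs:

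1. Use participants with at least one reported post-Baseline result as the denominator for total ADA prevalence, as is already done for incidence.
2. Require at least one reported post-Baseline result for class 1, and state the same for class 3. Anyone without one goes to class 6. Classes 2, 4 and 5 need no change here, since each already requires a post-Baseline positive.
3. Keep the 16-week limit as an additional condition, which serves longer-treated participants.

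The cost is a few lines of text and a change to the ADaM derivation; no new data are needed. A few participants may move from class 1 to Inconclusive, so the ADA-negative percentage may look less favourable.

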10 EFFICACY ANALYSES

10.1 Antitumor activity

The analysis of antitumor activity is exploratory in Part A of this study.

10.1.1 Definitions of the antitumor activity endpoints

The following endpoints are defined based on RECIST (Version 1.1) which standardizes solid tumor measurements and provides guidelines for the objective assessment of changes in tumor size during anti-cancer treatment.

Appendix 9 (Section 11.9) of the protocol contains the RECIST 1.1 guidelines to be used in this study, adapted from Eisenhauer (2009), and includes the definitions of target and non-target lesions, the definitions of target and non-target lesion responses at each tumor assessment, the criteria for determining overall tumor response at each tumor assessment based on target lesion response, non-target lesion response and the presence/absence of new lesions, and a participant's best overall response (BOR).

At each post-Baseline tumor assessment, the investigator will record responses for target lesions and non-target lesions, whether or not there has been an appearance of any new lesions, and the participant's overall tumor response based on their target lesion response, non-target lesion response and the presence/absence of new lesions. Note that target lesion response and non-target lesion response assessments will be based on the changes in the pre-existing lesions at Baseline and the appearance of new lesions will only factor in the determination of an overall tumor response of PD at that tumor assessment visit (i.e. per Tables A and B in Section 11.9.2 of Appendix 9 of the protocol).

Objective response rate (ORR) is defined as the percentage of participants with a BOR of complete response (CR) or partial response (PR) during Part A.

Disease Control Rate (DCR) is defined as the percentage of participants with a BOR of CR, PR, or stable disease (SD) during Part A.

Best overall response (BOR) is defined for each study participant as the best overall tumor response from each tumor assessment (scheduled and unscheduled assessments performed between Days 21 and 28 of every even cycle of study treatment) according to the RECIST criteria for changes in target and non-target lesions and the appearance of new lesions. Best overall response is determined from the start of study treatment until documented objective disease progression or the date of subsequent anti-cancer therapy (systemic therapy, surgery or radiotherapy for cancer), whichever occurs first. If anti-cancer therapy is started on the same day as a tumor assessment, then the overall response from that assessment will be used in the derivation of BOR. For a BOR of SD, a participant's tumor measurements must have met the SD criteria at least once after the start of study treatment at a minimum interval of no less than 6–8 weeks (42–56 days).

For Part A of this study, BOR determination requires confirmation of CR or PR responses at a subsequent assessment ≥ 4 weeks (28 days) after the criteria for CR or PR responses are first met. In addition, Table C in Appendix 10.9 of the protocol provides the derivation of BOR when confirmation of CR and PR responses are required. Confirmed BOR and unconfirmed BOR will be derived programmatically based on the overall tumor assessment data recorded on the eCRF

by the investigator and using the detailed guidance included in the Derivation of Efficacy Endpoints document Version 0.6 (dated 21 January 2022).

Duration of response (DOR) will be calculated for participants with a confirmed BOR of CR or PR as the time in days from the start date of the confirmed CR or PR to the first date that recurrent or progressive disease is objectively documented (i.e. according to the RECIST guidelines). This will be referred to as the duration of confirmed response and the following calculation will be performed:

$$\begin{aligned} & \text{Duration of Confirmed Response} \\ & = (\text{Date of First Objective Disease Progression} \\ & \quad - \text{Start Date of Confirmed CR or PR Response}) + 1 \end{aligned}$$

Duration of response will also be calculated for participants with an unconfirmed BOR of CR or PR (which may either be confirmed at a later tumor assessment or unconfirmed) as the time in days from the start date of the CR or PR to the date of the first documented objective disease progression (i.e. according to the RECIST guidelines). The following calculation will be performed:

$$\begin{aligned} & \text{Duration of Unconfirmed Response} \\ & = (\text{Date of First Objective Disease Progression} \\ & \quad - \text{Start Date of CR or PR Response}) + 1 \end{aligned}$$

For the purpose of a sensitivity analysis of both duration of confirmed response and duration of unconfirmed response, the above calculations will take into consideration the occurrence of both objective disease progression (per RECIST 1.1) and clinical disease progression (as described in Appendix 11.9 of the protocol and as determined by the investigator and recorded as a reason for study treatment discontinuation on the eCRF), whichever occurs first. If clinical disease progression occurs on the same date that a participant's objective disease progression is determined, then the participant will be included in the sensitivity analyses as having objective disease progression.

The following calculations will therefore be performed for the sensitivity analyses:

$$\begin{aligned} & \text{Duration of Confirmed Response} \\ & = (\text{Date of First Objective or Clinical Disease Progression} \\ & \quad - \text{Start Date of Confirmed CR or PR Response}) + 1 \end{aligned}$$

$$\begin{aligned} & \text{Duration of Unconfirmed Response} \\ & = (\text{Date of First Objective or Clinical Disease Progression} \\ & \quad - \text{Start Date of CR or PR Response}) + 1 \end{aligned}$$

For participants who die without objective disease progression, duration of confirmed response and duration of unconfirmed response will be censored on the date of death, regardless of cause. For a participant who discontinues early from Part A of the study with no objective disease progression, duration of confirmed response and duration of unconfirmed response will be censored on the date of their last available (scheduled or unscheduled) tumor assessment at which a lack of objective disease progression was determined. Participants who discontinue study treatment but who do not have documented objective disease progression (i.e. according to the RECIST guidelines), duration of confirmed response and duration of unconfirmed response will be censored at the date of their last available (scheduled or unscheduled) tumor assessment

at which a lack of objective disease progression was determined. Such participants might include those that are ongoing in Part A at the time of any defined data cut-off.

In the sensitivity analyses of duration of confirmed response and duration of unconfirmed response, the same censoring rules will apply except that the date of last contact will be used for the censoring of participants who discontinue early from Part A, complete Part A of the study or are ongoing in the study at a data cut-off for Part A without objective disease progression, clinical disease progression or death.

Date of last contact will be the latest of the dates of premature study termination and of last contact recorded on Study Termination eCRF page, the date of death, the date of last dose of study treatment, the dates of all visits, AE start and end dates (with partial dates imputed as earliest possible) and the date of contact recorded on the Survival Safety Follow-up and Survival Final Follow-up eCRF forms.

Further details on the derivation of duration of confirmed response and duration of unconfirmed response are included in the Derivation of Efficacy Endpoints document Version 0.6 (dated 21 January 2022).

Progression-free survival (PFS) will be calculated as the time in days from the first dose of study treatment to the date of the first documented objective disease progression (i.e. according to the RECIST guidelines), or death due to any cause, whichever occurs first. The following calculation will be performed:

$$PFS = (Date\ of\ Objective\ Progressive\ Disease/Death - Date\ of\ First\ Dose) + 1$$

Participants who die due to any cause without a documented objective disease progression will be considered to have progressed on the date of their death. Participants who do not have any post-Baseline tumor assessments will be censored on the date of their first dose of study treatment. Participants who discontinue early from Part A or discontinue study treatment without documented objective disease progression or death, will be censored on the date of their last available (scheduled or unscheduled) tumor assessment at which a lack of objective disease progression was determined. Participants who start anti-cancer therapy during Part A without a prior documented objective disease progression will be censored on the date of their last available (scheduled or unscheduled) tumor assessment prior to the initiation of the subsequent anti-cancer therapy. If anti-cancer therapy starts on the same date as the participant's tumor assessment and determination of objective disease progression, or the participant's death (due to any cause), then the participant will not be censored and the participant will be included as having an uncensored event on this date. This censoring rule will also be applied to participants who are ongoing at any data cut-off for an analysis of Part A data who have no documented objective disease progression. The use of anti-cancer therapy during Part A will be identified via ongoing medical review of the concomitant medications together with the start dates of further anti-cancer therapy information recorded on the survival follow-up pages of the eCRF.

As a sensitivity analysis, PFS will also be calculated as the time in days from the first dose of study treatment to the date of the first documented objective disease progression (per RECIST 1.1), the date of clinical disease progression, as determined by the investigator, or the date of death due to any cause, whichever occurs first. Last contact date (as defined above for DOR) will be used for the censoring of participants still alive with no reported disease progression

(objective or clinical). The same rules described above for the censoring of participants who start anti-cancer therapy will be applied in this sensitivity analysis.

Further details on the derivation of PFS are included in the Derivation of Efficacy Endpoints document Version 0.6 (dated 21 January 2022).

Overall survival (OS) will be calculated as the time in days from the date of first dose of study treatment to the date of death from any cause. Participants will be followed up to ascertain their survival status at the SFU visit (within 30 days after their last dose of study treatment) and at the Final Visit (3 months after their last dose of study treatment); they will not be followed up beyond this timepoint.

The following calculation will be performed:

$$OS = (Date\ of\ Death - Date\ of\ First\ Dose\ of\ Study\ Treatment) + 1$$

For participants who discontinue early from Part A of the study or who discontinue study treatment due to disease progression but continue in the study, who complete the Part A, or who are ongoing in the study at a data cut-off for Part A, but are not known to have died, OS will be censored on the date of their last contact.

